We recruited 46 adult patients affected by disturbing tinnitus lasting for at least 3 years. All were treated with a combined counseling protocol constituting hypnotherapeutic and muscle relaxation techniques. We randomly assigned 26 patients to the group receiving low-level laser stimulation treatment and 20 to the placebo group. The laser power was 5 mV and the wavelength 650 nm. The irradiation lasted 20 minutes daily for 3 months. The Tinnitus Handicap Inventory (THI) questionnaire was submitted at the beginning and at the end of treatment. The THI scores improved in the entire sample after treatment but more significantly in the group receiving low-level laser stimulation. From the point of view of clinical classification, **approximately 61% of irradiated patients had tinnitus severity decreased by one class, in comparison to 35% of the placebo group.**

Laser irradiation of the guinea pig basilar membrane.

Lasers Surg Med. 2004;35(3):174-80.

Wenzel GI, Pikkula B, Choi CH, Anvari B, Oghalai JS.

Bobby R. Alford Department of Otorhinolaryngology & Communicative Sciences, Baylor College of Medicine, Houston, Texas 77030, USA.

BACKGROUND AND OBJECTIVES: The cochlea is the part of the inner ear that transduces sound waves into neural signals. The basilar membrane, a connective tissue sheet within the cochlea, is tonotopically tuned based on the spatial variation of its mass, stiffness, and damping. These biophysical properties are mainly defined by its constituent collagen fibers. We sought to assess the effect of laser irradiation on collagen within the basilar membrane using histological analysis.

STUDY DESIGN/ MATERIALS AND METHODS: Four excised guinea pig cochleae were stained with trypan blue. From these, two were irradiated with a 600 nm pulsed dye laser and two were used as controls. Collagen organization was visualized using polarization microscopy.

RESULTS: Laser irradiation reduced the birefringence within the basilar membrane as well as within other stained collagen-containing structures. Larger reductions in birefringence were measured when more laser pulses were given. The effects were similar across all turns of each cochlea.

CONCLUSIONS: **Laser irradiation causes immediate alterations in collagen organization within the cochlea that can be visualized with polarization microscopy. These alterations may affect cochlear tuning.** Ongoing research is aimed at analyzing the effect of laser irradiation on cochlear function. It is conceivable that this technique may have therapeutic benefits for patients with high-frequency sensorineural hearing loss.

Assessing The Autonomic Effect Of Vagal Nerve Stimulation With Low Level Lasers By Heart Rate Variability

Journal of Neurology. 21. 1-6. 10.5580/IJN.54164.

Machado, Calixto & Machado, Y & Chinchilla, Mauricio & Foyaca-Sibat, Humberto. (2019). Vagus nerve stimulation (VNS) has been approved to treat refractory epilepsy, and for other conditions. The invasive nature of the electrical stimulus, which requires surgical implantation of electrodes around the cervical vagus nerve, is a technical limitation. The low-level laser therapy (LLLT) is actually considered a non-invasive technique, and has been increasingly used in diverse areas of medical practice. We developed a pilot study using LLLT for VNS in normal subjects, and assessing its effect on the autonomic nervous system (ANS) by the heart rate variability (HRV) methodology. Fifteen normal participants from 22 to 46 years, divided in three groups of 5 subjects each, paired in age and gender, were studied applying VNS using LLLT by lasers of different frequencies: RED Laser (in 5 subjects); VIOLET Laser (5 subjects); and RED/VIOLET Laser (5 subjects). The study included three experimental conditions: Basal record (10 minutes), VNS (10 minutes), and Post-VNS (10 minutes). The LF/HF ratio was considered, because it provides a measurement of the parasympathetic/sympathetic balance. When the RED laser was used for VNS there was a predominance of the parasympathetic activity. On the contrary, the stimulus with VIOLET laser provoked a sympathetic prevalence. Similarly, to the stimulus with the RED laser, when the RED/VIOLET laser was applied there was a predominance of the parasympathetic activity. **As a conclusion, this study showed that VNS using LLLT is a non-invasive and safe method, and should be considered for future protocols to recover parasympathetic/sympathetic nervous system balance in different conditions.**

Transmeatal cochlear laser (TCL) treatment of cochlear dysfunction: a feasibility study for chronic tinnitus.

Lasers Med Sci. 2003;18(3):154-61.

Tauber S, Schorn K, Beyer W, Baumgartner R.

Low-level-laser-therapy (LLLT) targeting the inner ear has been discussed as a therapeutic procedure for cochlear dysfunction such as chronic cochlear tinnitus or sensorineural hearing loss. Former studies demonstrate dose-dependent biological and physiological effects of LLLT such as enhanced recovery of peripheral nerve injuries, which could be of therapeutic interest in cochlear dysfunction. To date, in patients with chronic tinnitus mastoidal and transmeatal irradiation has been performed without systematic dosimetric assessment. However, light-dosimetric studies on human temporal bones demonstrated that controlled application of laser light to the human cochlea depends on defined radiator position within the external auditory meatus. This feasibility study first presents a laser application system enabling dose-controlled transmeatal cochlear laser-irradiation (TCL), as well as preliminary clinical results in patients with chronic cochlear tinnitus. The novel laser TCL-system, consisting of four diode lasers ($\lambda=635$ nm-830 nm) and a new specific head-set applicator, was developed on the basis of dosimetric data from a former light-dosimetric study. In a preliminary clinical study, the TCL-system was applied to 35 patients with chronic tinnitus and sensorineural hearing loss. The chronic symptoms persisted after standard therapeutic procedures for at least six months, while retrocochlear or middle-ear pathologies have been ruled out. The patients were randomized and received five single diode laser treatments ($\lambda=635$ nm, 7.8 mW cw, n=17 and $\lambda=830$ nm, 20 mW cw, n=18) with a space irradiation of 4 J/cm² site of maximal cochlear injury. For evaluation of laser-induced effects complete otolaryngologic examinations with audiometry, tinnitus masking and matching, and a tinnitus-self-assessment were performed before, during and after the laser-irradiation. **The first clinical use of the TCL-system has been well tolerated without side-effects and produced no observable damage to the external, middle or inner ear. Changes of tinnitus loudness and tinnitus matching have been described. After a follow-up period of six months tinnitus loudness was attenuated in 13 of 35 irradiated patients, while two of 35 patients reported their tinnitus as totally absent. Hearing threshold levels and middle ear function remained unchanged.** Further investigations by large double-blind placebo-controlled studies are mandatory for clinical evaluation of the presented TCL-system and its therapeutic effectiveness in acute and chronic cochlear dysfunction.

JUSTIFICATION FOR THE CURRENT CLINICAL STUDY

Tinnitus is a chronic problem affecting about one in every ten Americans. The persistent perception of sound is not only annoying and bothersome, but can affect multiple aspects of an individual's life, disrupting communication and sleep, and causing emotional and social disturbances such as anxiety and depression. At present, there is no cure for tinnitus and most treatment or management options are of limited short-term benefit restricted to the time of application. Low level laser therapy, such as through application of the Erchonia HLS™ Laser, has been shown through numerous prior trials and FDA clearances to effect positive change in numerous areas, including symptom perception arising from neurocognitive disruptions through its inflammatory reduction and neuromodulation properties. Therefore, it follows that application of Erchonia LLLT may help to alleviate the severity of tinnitus symptoms, providing a simple, non-invasive, safe, effective and side-effect free alternative therapy to reducing the severity of symptoms of tinnitus in affected individuals.

STUDY DESIGN

This pilot study is a non-blinded, two-group evaluation of the effect of the Erchonia® HLS™ on providing relief from the symptoms of tinnitus.

SUBJECT GROUPS

There will be two subject groups (Group A and Group B) in this pilot study. All subjects in both groups will be test subjects; that is, all study subjects will receive the active Erchonia® HLS laser device. The only difference between subject groups will be the anatomical area(s) where the Erchonia® HLS laser device is applied.

NON-BLINDED DESIGN

This pilot study will be non-blinded, such that both subjects and the investigator(s) will be aware that they are receiving the study procedures with active (true) Erchonia® HLS laser device.

NON-RANDOMIZED

As this pilot study wherein, all subjects receive the active procedure administrations, this is a non-randomized study design. The Investigator will assign 5 subjects to Group A and 5 subjects to Group B.

SUBJECTS

Recruitment

Subjects will be recruited from among the Principal Investigator's/test site's pool of patients who are currently being treated for, or who are seeking treatment for the symptoms of tinnitus, or from response to the following recruitment materials.

- a) Flyer

WANTED

**ADULTS WITH TINNITUS ONGOING
OVER THE LAST 6 MONTHS FOR A
CLINICAL STUDY OF THE EFFECTS OF
LOW LEVEL LASER LIGHT ON
REDUCING TINNITUS SYMPTOMS**

THIS STUDY INVOLVES 8 WEEKS OF SELF-ADMINISTERED LASER LIGHT PROCEDURES WITH THE ERCHONIA® HLS™ LASER AT YOUR HOME

FOR MORE INFORMATION PLEASE CONTACT:

<PI name>
<test site name & location>
<phone # and/or e-mail>

b) Newspaper Ad

**Tinnitus
Research Study**

This study is to see if the Erchonia® HLS™, a non-invasive, investigational device that uses low-level laser light, can help to relieve tinnitus that has been ongoing for at least 6 months.

The study involves 8 weeks of self-administered at home treatments.

Please contact <PI name> at
<test site name & location> at
<phone and/or e-mail> for details.

Compensation

A subject will not receive financial compensation for his or her participation in this clinical study.

A subject will not be charged for the cost of the study procedures with the Erchonia® HLS™ Laser or for the cost of any other directly-related evaluations or measurements that occur as part of his or her participation in the study.

Sample size

There will be 10 qualified subjects enrolled in this pilot study, all receiving active procedures. 5 subjects will be assigned to Group A and 5 subjects to Group B.

STUDY PROCEDURE

STUDY TEST BATTERY

The following is a list and description of the study assessment tools to be used and the variables to be recorded in this clinical study. At each evaluation point, the precise tools and variables from this list that will be employed will be specified.

BASELINE VARIABLES

A. *Tinnitus Variables*

- Diagnosed etiology of tinnitus, if known. *Responses:* presbyacusis, noise-induced, unknown.
- Number of months/years since tinnitus onset.
- Location of tinnitus. *Responses:* unilateral - right ear, unilateral - left ear, bilateral - both ears, nonspecific (generally inside the head).

B. *Medication and Treatment*

- *Prior treatment approaches for tinnitus reduction:* Record all prior treatments, whether conventional or alternative, tried by the subject for tinnitus reduction.
- *Concomitant Medication and Therapy Use:* Record all over-the-counter and prescription medications currently used for any indication (other than the management of tinnitus symptoms)

C. *Subject Demographics:* Subject age, gender and ethnicity are recorded.

OUTCOME ASSESSMENT TOOLS

PRIMARY OUTCOME MEASURE:

Tinnitus Handicap Inventory (THI)

The Tinnitus Handicap Inventory (THI) (Newman et al, 1996, Newman et al, 1998) is a 25-item self-report questionnaire that has Functional, Emotional and Catastrophic subscales. It has excellent convergent validity, construct validity and test-retest reliability. The THI takes 10 minutes to complete.

The individual responses to each of the 25 items are recorded as follows:

- ✓ Yes: 4
- ✓ Sometimes: 2
- ✓ No: 0

Individual scores for each question are added for the total THI score ranging from 0 to 100.

Another way of looking at the results of the THI is by Grade determination, as follows:

- *Grade 1 - slight - (THI 0-16)* – Tinnitus only heard in quiet environment, very easily masked. No interference with sleep or daily activities; generally pertains to individuals who are experiencing but are not troubled by tinnitus.
- *Grade 2 - mild - (THI 18-36)* – Tinnitus easily masked by environmental sounds and easily forgotten with activities. May occasionally interfere with sleep but not daily activities.

- *Grade 3 - moderate - (THI 38-56)* – Tinnitus may be noticed even in the presence of background or environmental noise although daily activities may still be performed. Less noticeable when concentrating. Not infrequently interferes with sleep and quiet activities.
- *Grade 4 - severe - (THI 58-76)* – Tinnitus almost always heard, rarely if ever masked. Leads to disturbed sleep pattern and can interfere with ability to carry out normal daily activities. Quiet activities adversely affected. Hearing loss is likely present, but its presence is not essential.
- *Grade 5 - catastrophic - (THI 78-100)* - All tinnitus symptoms at level of severe or worse. Should be documented evidence of medical consultation. Hearing loss is likely present, but its presence is not essential. Associated psychological pathology is likely to be found in hospital or general practitioner records. Given the epidemiological data, grading in this group should be extremely rare.

SECONDARY OUTCOME MEASURES:

Numerical Rating Scale (NRS)

The Numerical Rating Scale (NRS) will be used to capture the self-reported daily impact of Tinnitus Annoyance and Tinnitus Loudness. Zero represents 'no impact at all' whereas the upper limit represents 'the worst impact ever possible'.

NUMERICAL SCALE: TINNITUS ANNOYANCE

How does the subject rate his or her tinnitus annoyance on a scale of 1 to 100? With 1 being "No Annoyance" and 100 being "Worst possible Annoyance".

TINNITUS ANNOYANCE SCORE: _____ /100

NUMERICAL SCALE: TINNITUS LOUDNESS

How does the subject rate his or her tinnitus loudness on a scale of 1 to 100? With 1 being "No Loudness" and 100 being "Worst possible Loudness".

TINNITUS LOUDNESS SCORE: _____ /100

Subject Satisfaction with Study Outcome

The subject is asked to rate how satisfied he or she is with any change in his or her overall tinnitus following completion of the laser administration procedures with the Erchonia® FX-635™ by using the 5-point Likert scale presented below to respond to the following question: "Overall, how satisfied or dissatisfied are you with any change in your tinnitus following the study procedures with the study laser device?"

- Very Satisfied
- Somewhat Satisfied
- Neither Satisfied nor Dissatisfied
- Not Very Satisfied
- Not at All Satisfied

STUDY PROCEDURE PROTOCOL

PRE-PROCEDURE ACTIVITIES

Pre-procedure activities will be conducted remotely over videoconference or telemedicine.

STUDY QUALIFICATION

SIGNING OF INFORMED CONSENT FORM

The participant will be sent an electronic version of the Informed Consent Form. The PI will remotely video conference with the prospective research participant, presenting and reviewing in detail the items in the informed consent form with the individual and answering any questions he or she may have. When finished, the researcher and participant will electronically sign the consent form and print or download the signed document for archiving.

ASSIGNMENT OF SUBJECT IDENTIFICATION NUMBER

The subject is assigned a unique subject identification number based upon his or her order of entry into the study.

Additional information about the informed consent and subject ID number assignment is contained in a later section of the protocol titled, "SAFETY AND CONFIDENTIALITY ISSUES."

STUDY QUALIFICATION EVALUATION: INCLUSION/EXCLUSION CRITERIA

INCLUSION CRITERIA

To be eligible for study participation, a subject must satisfy each of the following criteria.

- Subjective tinnitus
- Tonal tinnitus.
- Constant tinnitus on-going at least half the time over at least the past 6 months.
- Willing to abstain from other tinnitus-related treatments except prior hearing aid use throughout the study duration.
- Willing and able to refrain from activities or work involving excessive noise exposure without the use of effective hearing protection throughout study participation.
- 18 years of age or older
- Primary language is English

EXCLUSION CRITERIA

A subject who satisfies any of the following criteria will be excluded from study participation:

- Objective tinnitus
- Atonal, pulsatile, intermittent, or occasional tinnitus
- Severe or profound hearing loss in one or both ears
- Current or prior surgically removed acoustic neuroma
- Consistent use of any of the following drugs known to cause or increase tinnitus (primarily ototoxins) within the past 30 days:
 - ✓ NSAIDS (motrin, naproxen, relafen, etc)
 - ✓ aspirin (exceeding 300mg per day) and other salicylates
 - ✓ Lasix and other "loop" diuretics
 - ✓ "mycin" antibiotics such as vancomycin
 - ✓ quinine and related drugs
 - ✓ Chemotherapy agents such as cis-platin
- Acute or chronic vertigo/dizziness
- Ménière's disease
- Prior stapedectomy
- Prior mastoidectomy
- Auditory nerve tumor (acoustic neuroma), current or surgically removed in the past
- Active infection/wound/external trauma to the areas to be treated with the laser
- Medical, physical or other contraindications for, or sensitivity to, light therapy
- Pregnant, breast feeding, or planning pregnancy prior to the end of study participation
- Developmental disability or cognitive impairment that in the opinion of the investigator would preclude adequate comprehension of the informed consent form and/or ability to record the necessary study measurements

INCLUSION CRITERIA PART 2

- Total THI score is **38 (Grade 3) or greater.**
- Numerical Rating Scale (NRS): Tinnitus Annoyance is **40 out of 100 or greater.**
- Numerical Rating Scale (NRS): Tinnitus Loudness is **40 out of 100 or greater.**

SUBJECT GROUP ASSIGNMENT

A fully qualified subject is assigned by the investigator to Procedure Group A or to Procedure Group B.

PRE-PROCEDURE EVALUATION PHASE

The pre-procedure evaluation phase commences following successful study qualification, on the same day or another day. During pre-procedure evaluation, the following is recorded over videoconference or telemedicine:

BASELINE VARIABLES

- Tinnitus Variables
- Medication and Treatment

- Subject Demographic

[figure not shown]
PROCEDURE ADMINISTRATION PHASE

The qualified subject will be shipped a Erchonia® HLS™ device, that is preset and cannot be altered by the end user. Additionally, the subject will be shipped Erchonia® HLS™ Operation Manual and Treatment Log Form that corresponds to the subject's assigned treatment group (A or B). The procedure administration phase lasts 8 weeks and comprises 56 procedure administrations with the Erchonia® HLS™ administered by the subject at home: daily procedure administrations for 8 weeks.

PROCEDURE ADMINISTRATION PROTOCOL

- The procedure administration phase of the study commences following completion of the pre-procedure phase, on the same day or up to 15 days later.
- The procedure administration phase extends over 8 consecutive weeks.
- Each subject receives 56 total procedures with the Erchonia® HLS™: daily procedure administrations for 8 weeks.
- Each procedure administration lasts 10 minutes.
- Each procedure administration is completed at the subject's home.
- Each subject will be provided an at home "Operation Manual" that details the laser use and treatment administration.
- Each subject will be provided at home "Treatment Log Forms" to document each time the treatment is administered.

- **Group A: Procedure administration protocol is as follows:**
 1. The subject is correctly fitted with the provided safety goggles.
 2. The Erchonia® HLS laser is held at approximately 4 inches from the skin throughout the entire treatment.
 3. The Erchonia® HLS™ is then activated for 5 minutes.
 4. The laser treatment begins approximately 1 inch above the right ear and applied in a slow continuous sweeping motion down the right side of the neck and then proceed back to top of ear. This back and forth sweeping motion is performed for 5 continuous minutes.

[figure not shown]
5. Step 4 is then repeated over the left side of head and left side of neck. Both the right and left side will receive 5-minute treatment each.
6. The subject's protective eyewear is then removed, and the session is over.

➤ **Group B: Procedure administration protocol is as follows:**

- This is an alternating treatment protocol, such as the subject will apply the laser treatment to the head on days 1 and 2, and on day 3 the laser is applied to the midsection. This 3-day rotation is followed throughout the 8 weeks and is detailed in the subjects “Treatment Log Forms”.
 1. The subject is correctly fitted with the provided safety goggles.
 2. The Erchonia® HLS laser is held at a distance of approximately 4 inches from the skin throughout the entire treatment.
 3. The Erchonia® HLS™ is then activated for 5 minutes.

Group B, Head Treatment is applied as follows:

[figure not shown]
- 4. The laser treatment begins approximately 1 inch above the right ear and applied in a slow continuous sweeping motion down to the center of the ear and then proceed back to top of ear. This back and forth sweeping motion is performed for 5 continuous minutes.

[figure not shown]
- 5. Step 4 is then repeated over the left side of head and ear. Both the right and left side will receive 5-minute treatment each.
- 6. The subject's protective eyewear is then removed, and the session is over.

Group B, Mid-Section Treatment is applied as follows:

- 7. The laser treatment begins above the umbilicus and applied in a slow continuous sweeping motion up the right side of the neck (vagus nerve) and then proceed back to umbilicus. This back and forth sweeping motion performed for 5 continuous minutes.

- 8. Step 4 is then repeated over the left side of midsection. Both the right and left side will receive 5-minute treatment each.

9. The subject's protective eyewear is then removed, and the session is over.

PROCEDURE ADMINISTRATION PHASE MEASURES

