8 WEEK EVALUATION: STUDY ENDPOINT

Following 8 weeks of study procedure administrations with the Erchonia® HLS™, the following will be recorded over videoconference or telemedicine with the site investigator and subject as outlined in the STUDY TEST BATTERY section above. These recordings will form the study endpoint data set from which change from baseline will be evaluated with respect to assessing study outcome.

- Tinnitus Handicap Inventory (THI)
- Numerical Rating Scale (NRS): Tinnitus Loudness
- Numerical Rating Scale (NRS): Tinnitus Annoyance
- Subject Satisfaction With Study Outcome
- Adverse Events Evaluation

ADVERSE EVENTS

At any time throughout the duration of the clinical trial that is necessary, any and all potential adverse events reported by a subject will be reported to the investigator and will be recorded on the case report form, and subsequently evaluated by a suitably qualified independent reviewer for determination of relationship to the study treatment and whether or not any corrective action needs to be taken. All potential adverse events recorded will be appropriately reported to the governing IRB, as applicable.

It is unlikely and not expected that any adverse events will result from implementation of this clinical study protocol. Prior clinical trials using low level laser light have not typically yielded any adverse events or reactions. However, potential adverse events that may feasibly occur from application of

the Erchonia® HLS™ include, but are not necessarily limited to: skin irritation, discoloring, rash, indentations and infection.

PRIVACY AND CONFIDENTIALITY

Records for each subject in this clinical study will be maintained in separate files in a locked filing cabinet at the respective test site. The investigator at the test site will be responsible for ensuring that all records for a subject pertaining to his or her participation in the clinical study are maintained in the subject's file at all times other than when information is being recorded on them.

Copies of all subject case report forms will be made and supplied to Regulatory Insight, Inc. and Erchonia Corporation. Regulatory Insight, Inc. and Erchonia Corporation will maintain these copies in a separate clinical study file that is kept in a locked filing cabinet on their respective premises. The original records will be maintained at the respective test sites.

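### The investigator chooses Group A or B after the entry scores can be known; a concealed 5:5 list would cheaply remove selection bias from the exploratory A-versus-B look

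*Combined protocol and SAP*

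**What the plan says.** Under STUDY DESIGN, NON-RANDOMIZED, the protocol gives one reason for its allocation method: "As this pilot study wherein, all subjects receive the active procedure administrations, this is a non-randomized study design". The next sentence reads "The Investigator will assign 5 subjects to Group A and 5 subjects to Group B". The Sample size paragraph repeats the split ("5 subjects will be assigned to Group A and 5 subjects to Group B").

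SUBJECT GROUP ASSIGNMENT sets the timing: "A fully qualified subject is assigned by the investigator to Procedure Group A or to Procedure Group B". Qualification includes INCLUSION CRITERIA PART 2, which requires "Total THI score is 38 (Grade 3) or greater" and scores of at least 40 out of 100 on both NRS items. Order of entry fixes the subject ID only. No assignment rule, sequence, stratification or concealment is described.

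On analysis, EXPECTED RESULTS anticipates a reduction compared with baseline, and the 8-week section says "These recordings will form the study endpoint data set from which change from baseline will be evaluated with respect to assessing study outcome". STATISTICAL ANALYSIS sets no success criteria and describes an exploratory aim whose results may help in developing a controlled study. Its Co-Variate Evaluation paragraph says procedure group will be considered. Statistical Procedures plans descriptive presentation, with an optional ANCOVA.

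**The concern.** The reason given does not support the choice made. If all subjects receive active laser, there is no sham group to randomise against. There are still two procedures, differing in where the laser is applied, and subjects could be randomised between them. The protocol's own Supporting Materials show this: the transmeatal laser feasibility study treated all 35 tinnitus patients with active laser at one of two wavelengths (17 and 18 patients), and its abstract says "The patients were randomized and received five single diode laser treatments".

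The person who chooses the group can know the subject's entry THI and NRS scores. Because subjects may come from the investigator's own patients, that person may also know history that is not recorded as a baseline variable. If the choice follows severity, regression to the mean makes the more severe group appear to improve more, even if neither procedure works. If it follows an unrecorded factor, no baseline adjustment can remove the bias. What is at stake is the side-by-side view of A and B that could be carried into the design of a later study.

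**Working it through.** **The plan's own figure.** The only figure is the sample size: 5 + 5 = 10, which agrees wherever it appears. It is given without alpha, power, effect size or SD, so there is no power calculation to reproduce.

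**Inputs from the protocol.** Five subjects per group; THI from 0 to 100; entry at THI 38 or more.

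**Assumed inputs (not in the documents).** THI mean 45 and SD 22 before the entry cut; test-retest correlation r = 0.9, 0.8 or 0.7; no treatment effect. By simulation, qualifying subjects then have mean THI about 58 and SD 13.8.

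**Baseline gap.** The top five of ten normal scores exceed the bottom five by 1.48 SD on average. Perfect sorting by severity therefore gives about 1.48 × 13.8 = 20.4 points (simulated: 20.5 to 20.6). If the choice correlates 0.5 with THI, the gap is about half of that (simulated: 10.2 to 10.3).

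**Spurious difference in change** = (1 − r) × gap.
- Perfect sorting: 0.1 × 20.6 = 2.1; 0.2 × 20.5 = 4.1; 0.3 × 20.6 = 6.2.
- Partial selection: 0.1 × 10.2 = 1.0; 0.2 × 10.2 = 2.0; 0.3 × 10.3 = 3.1.

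**Sampling SD** ≈ 22 × √(1 − r²) × √(1/5 + 1/5). At r = 0.9 this is 9.59 × 0.632 = 6.06; at 0.8, 13.2 × 0.632 = 8.3; at 0.7, 15.7 × 0.632 = 9.9.

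**Simulation** (40,000 replicates per r; unadjusted A-B difference in THI change, absolute value; RMSE = √(bias² + SD²)):

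| Assignment | Bias, r = 0.9 / 0.8 / 0.7 | SD | RMSE |
|---|---|---|---|
| Random 5:5 list | 0.0 / 0.0 / 0.0 | as RMSE | 6.12 / 8.55 / 10.25 |
| Choice correlates 0.5 with THI | 1.05 / 2.01 / 3.11 | 6.10 / 8.52 / 10.16 | 6.19 / 8.76 / 10.63 |
| Perfect sorting by THI | 2.04 / 4.07 / 6.12 | 6.07 / 8.42 / 10.08 | 6.40 / 9.35 / 11.80 |

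The list's reduction in RMSE at r = 0.9 is 1 − 6.12/6.19 = 1% against partial selection and 1 − 6.12/6.40 = 4% against perfect sorting. At r = 0.7 the reductions are 1 − 10.25/10.63 = 4% and 1 − 10.25/11.80 = 13%. Changing the assumed mean and SD to 35/20, 55/22 or 45/25 moves the perfect-sorting bias to 1.8-2.3 at r = 0.9 and 5.0-6.7 at r = 0.7, with RMSE reductions of 3-15%.

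**Unrecorded factor.** Suppose the choice correlates 0.5 with a factor that itself correlates 0.3 with follow-up THI given baseline. The bias after baseline adjustment is about 0.5 × 1.48 × 0.3 × 9.59 = 2.1 points at r = 0.9 (simulated: 2.1 / 3.0 / 3.5). At a correlation of 0.1 it is 0.7 / 1.1 / 1.3. A random list has zero expected bias from this source as well.

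**What the list leaves.** The baseline gap under random 5:5 has SD 13.8 × 0.632 = 8.7. The mean absolute gap is then about 0.8 × 8.7 = 7 points, with about a 25% chance of a gap above 10. Over the 252 possible lists, someone tracking past assignments in an open study guesses 5 + (2¹⁰/252 − 1)/2 = 6.5 of 10 correctly, and on average the last 1.7 are certain.

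**The case against.** The strongest reply is that no planned inference is harmed. There are no success criteria, no A-versus-B hypothesis and no selection rule; the data are to be presented descriptively, and sampling error exceeds the bias from selection on severity in every scenario computed. All of that stands, and it limits the point to a modest one.

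Second, knowing the entry scores also lets an investigator balance the groups. A simulated investigator who balances THI sequentially reaches a mean absolute gap of 3.8 points against 6.9 for the random list, with RMSE no worse (6.11 / 8.41 / 9.98 against 6.15 / 8.52 / 10.27 in the same run). The Supporting Materials also include a vagus-nerve laser pilot with three groups of five paired on age and gender. This shows that a stated balancing rule would be defensible. The protocol states none, and balancing on THI does not protect against unrecorded factors.

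Third, the protocol calls THI test-retest reliability excellent. That favours the r = 0.9 column, where the bias from selection on severity is only 1 to 2 points. This is fair, although no coefficient is given.

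Four stronger readings are tempting but unsupported:
- A reader might infer that severe cases will be steered to one group. The documents do not say so; nothing prevents it.
- A reader might infer that the main result is compromised. The pooled change does not depend on who is in which group, unless the effect of the application area differs between kinds of subject.
- A reader might infer that this pilot will choose between A and B. The protocol says only that results may assist a later study.
- A reader might expect a large gain in precision. A reduction near 40% (1 − 6.56/11.04 at r = 0.9) appears only with perfect sorting combined with a baseline-adjusted A-versus-B model that the plan does not specify.

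**Conclusion.** The concern holds as a cheap improvement. Assignment is by investigator choice after the entry scores can be known, without rule or concealment, and the stated reason does not justify it. The exploratory A-versus-B look is therefore open to avoidable selection bias: about 1 to 3 THI points under partial selection and 2 to 6 in the worst case, against a sampling SD of 6 to 10. These sizes rest on the assumed THI distribution, the assumed r and the assumed strength of selection. The direction of the argument needs only that r is below 1 and that choice may follow severity or another prognostic factor.

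Randomisation would make the comparison unbiased with respect to recorded and unrecorded factors. It would not make five per group informative, and it would not touch open-label reporting bias in self-reported outcomes. A compulsory baseline covariate is not part of the recommendation. With a random list it raises RMSE from 6.12 / 8.55 / 10.25 to 6.56 / 9.09 / 10.72, which is above even unadjusted partial selection (6.19 / 8.76 / 10.63).

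**What to change.** In STUDY DESIGN, replace the NON-RANDOMIZED text with:

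> All subjects receive the active device; there is no sham group. Subjects are randomly assigned 5:5 to Group A or Group B from a computer-generated list prepared in advance, held by sponsor or monitor personnel outside the site, and released one assignment at a time after qualification is recorded.

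Change that heading and its contents entry to match. In SUBJECT GROUP ASSIGNMENT, have the qualified subject assigned by the next entry on the list. In STATISTICAL ANALYSIS, add that baseline THI and NRS scores are shown by group.

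If investigator assignment is kept, state the rule used, show baseline by group, and describe A-versus-B results as descriptive only.

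The cost is a ten-line list and a few sentences. No subjects, visits or devices are added, the sample-size sentence stands, and the group-specific log already ships after assignment. The downsides are an amended allocation text for the IRB and possibly a line in the consent form, plus the partial predictability of an open 5:5 list and the remaining chance imbalance sized above.
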